5.3.3 Activity

No special restrictions.

Amended Clinical Trial Protocol 12 SAR442168-EFC16645 - tolebrutinib 20-Dec-2023 Version number: 1

5.4 SCREEN FAILURES

Screen failures are defined as participants who consent to participate in the clinical study but are not subsequently randomly assigned to study intervention. A minimal set of screen failure information is required to ensure transparent reporting of screen failure participants to meet the Consolidated Standards of Reporting Trials (CONSORT) publishing requirements and to respond to queries from regulatory authorities. Minimal information includes demography, screen failure reasons, eligibility criteria, and any SAE.

Individuals who do not meet the criteria for participation in this study (screen failure) may be rescreened up to 2 times. Rescreened participants should be assigned a different participant number. More information on rescreening procedures is provided in the Study Manual.

5.5 CRITERIA FOR TEMPORARILY DELAYING ADMINISTRATION OF STUDY INTERVENTION

During a regional or national emergency declared by a governmental agency, if the site is unable to adequately follow protocol mandated procedures, contingency measures proposed in Appendix 10 (see Section 10.10) should be considered for screening, enrollment, randomization, and administration of study intervention.

6 STUDY INTERVENTION

Study intervention is defined as any investigational intervention(s), marketed product(s), or placebo intended to be administered to a study participant according to the study protocol.

6.1 CRITERIA FOR TEMPORARILY DELAYING ENROLLMENT AND ADMINISTRATION OF STUDY INTERVENTION

During a regional or national emergency declared by a governmental agency, if the site is unable to adequately follow protocol mandated procedures, contingency measures proposed in Appendix 10 (Section 10.10) should be considered for screening, enrollment, randomization, and administration of the study intervention.

6.2 STUDY INTERVENTION(S) ADMINISTERED

ARM name	SAR442168	Placebo	
Intervention name	SAR442168	Placebo	
Туре	Drug	Drug	
Dose formulation	Film coated tablet	Film coated tablet	
Unit dose strength(s)	60 mg	0 mg	
Dosage level(s)	Once daily	Once daily	
Route of administration	Oral	Oral	
Use	Experimental	Placebo	
IMP and NIMP	IMP	IMP	
Packaging and labeling	Study intervention will be provided in wallet blister packaging. Each wallet blister packaging will be labeled as per country requirements.	Study intervention will be provided in wallet blister packaging. Each wallet blister packaging will be labeled as per country requirements.	
Current name	SAR442168	Not applicable	

Table 2 - Overview of study interventions administered

IMP: investigational medicinal product; NIMP: noninvestigational medicinal product.

Between the protocol-scheduled on-site visits, interim visits may be required for IMP dispensing. As an alternative to these visits or to replace on-site IMP dispensation, if needed, SAR442168 may be supplied from the site to the participant via a Sponsor-approved courier company (direct-to-patient [DTP]) where allowed by local regulations and approved by the Sponsor.

6.2.1 Noninvestigational medicinal product

MRI contrast-enhancing preparations

- Route(s) of administration: IV
- Dose regimen: as per respective label

6.3 PREPARATION/HANDLING/STORAGE/ACCOUNTABILITY

- 1. The Investigator or designee must confirm appropriate temperature conditions have been maintained during transit for all study intervention received and any discrepancies are reported and resolved before use of the study intervention. In case of DTP shipment, temperature monitoring is under vendor responsibility.
- 2. Only participants enrolled in the study may receive study intervention and only authorized site staff may supply or administer study intervention. All study interventions must be stored in a secure, environmentally controlled, and monitored (manual or automated) area in accordance with the labeled storage conditions with access limited to the Investigator and authorized site staff.
- 3. The Investigator, institution, or the head of the medical institution (where applicable) is responsible for study intervention accountability, reconciliation, and record maintenance (ie, receipt, reconciliation, and final disposition records).

Any quality issue noticed with the receipt or use of an IMP (deficiency in condition, appearance, pertaining documentation, labeling, expiration date, etc) must be promptly notified to the Sponsor. Some deficiencies may be recorded through a complaint procedure (see Section 8.3.10).

A potential defect in the quality of IMP may be subject to initiation of a recall procedure by the Sponsor. In this case, the Investigator will be responsible for promptly addressing any request made by the Sponsor, in order to recall the IMP and eliminate potential hazards.

Under no circumstances will the Investigator supply IMP to a third party (except for DTP shipment, for which a courier company has been approved by the Sponsor), allow the IMP to be used other than as directed by this clinical trial protocol, or dispose of IMP in any other manner.

6.4 MEASURES TO MINIMIZE BIAS: RANDOMIZATION AND BLINDING

All participants will be centrally assigned to randomized study intervention using an interactive response technology (IRT). Randomization will be stratified by age at screening (>40, \leq 40 years) and geographic region (US versus non-US). A participant cannot be randomized more than once in the study. A participant assigned to a specific arm at randomization may be allocated, by the IRT, to several (varying) intervention numbers (and corresponding intervention kit numbers) for multiple visits despite having the same intervention arm assignment from randomization. That is, in these cases, the intervention/kit number varies but the arm assignment at randomization does not change. Before the study is initiated, the log in information and instructions for the Interactive Web Response System (IWRS) will be provided to each site.

Study intervention will be dispensed at the study visits summarized in the SoA (Section 1.3).

Returned study intervention should not be re-dispensed to the participants.

The Treating Investigator, Examining Investigator/rater, clinical site staff, and Sponsor's clinical trial team members will not have access to the randomization (treatment) codes. The IRT will be programmed with blind-breaking instructions. In case of an emergency, the Investigator has the sole responsibility for determining if unblinding of a participant's treatment assignment is

Amended Clinical Trial Protocol 12 SAR442168-EFC16645 - tolebrutinib 20-Dec-2023 Version number: 1

warranted (eg, in case of available antidote). Participant safety must always be the first consideration in making such a determination. If a participant's treatment assignment is unblinded, the Sponsor must be notified within 24 hours after breaking the blind. The date and reason that the blind was broken must be recorded in the source documentation and electronic case report form (eCRF), as applicable. If unblinded, information pertaining to the treatment allocation should not be shared with other members of the study team or Sponsor.

Methods of blinding

This study is blinded for assignment of SAR442168 and placebo. Tablets of SAR442168 and placebo will appear identical.

In order to maintain the study blind and ensure participant safety, each site will have 2 types of Investigators: A Treating Investigator and an Examining Investigator/rater (blinded). The study site personnel designated to conduct efficacy assessments (Examining Investigators/raters or other qualified site staff) must be different than physicians responsible for participants' medical management (Treating Investigators) in order to protect against possible unblinding of the treatment assignment during regular clinical care of participants. In view of the extended duration of this study, each site will identify primary and back-up Treating and Examining Investigators/raters. A Treating Investigator cannot change roles to Examining Investigator/rater during the study.

The Treating Investigator is the physician responsible for participant's care and should be a neurologist experienced in the care of MS patients. The Treating Investigator will not have access to efficacy data including EDSS scores other than the score at screening but will receive alerts on 6-month CDP. The Treating Investigator will have access to the participant's other collected data and will follow the participant, collect safety events, and make treatment decisions based on the participant's clinical response and laboratory findings. Once the participant has been randomly assigned to treatment, the Treating Investigator will use a local laboratory if needed for additional safety assessments.

The Examining Investigator/rater should be trained and certified in administering the EDSS and other efficacy tests. Details for certification and re-certification requirements for administering the EDSS will be provided in the Study Manual. The Examining Investigator/rater will be responsible for assessment of the EDSS including the screening EDSS score assessment and other clinical efficacy tests and will have access only to data needed for these assessments. The Examining Investigator/rater can delegate assessment of T25-FW, 9-HPT, SDMT and CVLT-II to qualified study staff. The Examining Investigator/rater will not have access to scores and prior EDSS assessments. Whenever possible, the same individual should perform the examinations for the full study duration. All efforts should be made to keep the Examining Investigator/rater blinded to a participant's treatment assignment, treatment dates, and consequently to AE data, non-neurological symptoms, laboratory data, concomitant and prior medications, and any other information not related to the EDSS and other efficacy assessments. Participants will be instructed not to discuss any symptoms related to the IMP with the Examining Investigator/rater; the Examining Investigator/rater will remind the participant of this at the start of the examination and will not ask any questions that are not related to the neurological examination. Participants will be asked not to communicate any co-medication used or symptoms unless requested by the Examining Investigator/rater for efficacy evaluation.

A DMC will be used to periodically monitor safety of this study. Unblinded data will be provided for DMC review by an unblinded independent statistician. Study team members, Investigators, and study participants will not have access to unblinded data.

6.5 STUDY INTERVENTION COMPLIANCE

- Methods used by the Investigator or his/her delegate to ensure that the IMP was administered may include mouth inspection (eg, for on-site visits).
- Measures taken to ensure study intervention accountability include the following:
 - Intervention units are returned by the participant at each visit. In case of direct-topatient process, the intervention units can be returned by the carrier (if defined in the contract).
 - The Treating Investigator or his/her delegate counts the number of tablets remaining in the returned packs and fills in the Intervention Log Form.
 - The Treating Investigator or his/her delegate records the dosing information on the appropriate page(s) of the eCRF.
 - The monitor in charge of the study then checks the eCRF data by comparing them with the IMP which he/she has retrieved and Intervention Log Form.

A paper diary, to capture the details of the use of study medication, timing of meals, change in mealtime for IMP administration, missed doses, and overdoses, will be provided to each study participant after they have received training on how to use the diary. Participants should bring the diary to each site visit for review by the Investigator and/or study staff and monitoring of compliance and exposure data. A new paper diary should be provided to the study participant at each visit when study medication will be dispensed. In case of DTP shipment, the new paper diary will be dispensed along with IMP, and the participant will return the previous completed paper diary to the study site via the carrier.

Participant compliance with study intervention will be assessed at each study site visit. Compliance will be assessed by counting returned tablets. Deviation(s) from the prescribed dosage regimen should be recorded in the eCRF.

When participants self-administer study intervention(s) at home, compliance with study intervention will be assessed at each visit. Compliance will be assessed by counting returned tablets during the site visits and documented in the source documents and eCRF. Deviation(s) from the prescribed dosage regimen should be recorded in the eCRF.

A record of the number of SAR442168 tablets dispensed to and taken by each participant must be maintained and reconciled with study intervention and compliance records. Intervention start and stop dates, including dates for intervention delays and/or dose reductions will also be recorded in the eCRF.

6.6 CONCOMITANT THERAPY

Any medication or vaccine (including over-the-counter or prescription medicines, vitamins, and/or herbal supplements) that the participant is receiving at the time of enrollment or receives during the study must be recorded along with:

- Reason for use.
- Dates of administration including start and end dates.
- Dosage information including dose and frequency.

Any live (attenuated) vaccine within 2 months before the first treatment visit and during the intervention period is prohibited.

Therapies for MS noted in the exclusion criterion E 06 are not permitted after randomization while the participant is on study treatment. Short-term use (3 to 5 days) of glucocorticoids (eg, for MS relapse treatment or an acute illness) and local corticosteroids (eg, topical, nasal, ocular, otic, intra-articular) are allowed.

The Medical Monitor should be contacted if there are any questions regarding concomitant or prior therapy.

Participants must abstain from taking prescription or nonprescription drugs (including vitamins and dietary or herbal supplements) within 7 days (or 14 days if the drug is a potential enzyme inducer) or 5 half-lives (whichever is longer) before the start of study intervention until completion of the follow-up visit, unless, in the opinion of the Investigator and Sponsor, the medication will not interfere with the study.

Medications for treatment of MS symptoms (eg, walking impairment, fatigue, spasticity, incontinence, pain) should be maintained at a stable dose prior to screening and for the duration of the treatment period, if clinically feasible.

Anticoagulant/antiplatelet therapies are not permitted to be taken concomitantly with the IMP, including the following:

- Acetylsalicylic acid (aspirin) >81 mg/day.
- Antiplatelet drugs (eg, clopidogrel).
- Warfarin (vitamin K antagonist).
- Heparin, including low molecular weight heparin (antithrombin agents).
- Dabigatran (direct thrombin inhibitor).
- Apixaban, edoxaban, rivaroxaban (direct factor Xa inhibitors).

Paracetamol/acetaminophen, at doses of ≤ 3 grams/day, is permitted for use at any time during the study. Short courses (up to 5 days) of nonsteroidal anti-inflammatory drugs (NSAIDs) (other than acetylsalicylic acid), preferably selective cyclooxygenase-2 inhibitors at the lowest effective dose, may be given during the study if clinically necessary for the treatment of an existing medical condition or a new event. The Investigator must record the use of NSAIDs (and any other comedication) in the eCRF.

CYP Inhibitors and Inducers:

Potent and moderate inducers of CYP3A or potent inhibitors of CYP2C8 hepatic enzymes are not permitted throughout the study (Appendix 9 [Section 10.9]).

Based on nonclinical drug metabolism studies, SAR442168 is a substrate of the CYP3A and CYP2C8 isoenzymes. In healthy participants, potent CYP3A4 inhibitor (itraconazole 200 mg once daily for 4 days) increased SAR442168 area under the curve AUC exposure 1.8-fold (Study INT16385) and potent CYP2C8 inhibitor (gemfibrozil 600 mg twice daily for 6 days) increased SAR442168 AUC exposure 8.4-fold (Study INT16726). Based on a satisfactory safety and tolerability profile and on the observed exposure in healthy participants who received SAR442168 at a dose of up to 240 mg SAR442168 once daily for 14 days under fed conditions (Study TDR16862), drugs that strongly inhibit CYP3A4 are allowed and drugs that strongly inhibit CYP2C8 are not permitted. In healthy participants, potent CYP3A4 and moderate CYP2C8 induction by rifampicin (600 mg once daily for 8 days) decreased SAR442168 exposure 6-fold (Study INT16726). Therefore, potent and also moderate (based on prediction) CYP3A inducers are not permitted due to their potential to decrease SAR442168 exposure and efficacy.

See Appendix 9 (Section 10.9) for the list of drugs to be avoided.

The Sponsor should be contacted if there are any questions regarding concomitant or prior therapy.

6.6.1 Open-label treatment

If a participant achieves the primary endpoint (6-month CDP), they may, in conjunction with the Treating Investigator, choose to receive one of the following:

- 1. To switch to open-label SAR442168 treatment; OR
- 2. To switch to a non-study treatment approved for NRSPMS in their respective country. In this case, the participant will permanently discontinue the IMP and will be encouraged to remain in the study for planned clinical visits (see Section 7.1.1) until common study end.

In case the participant switches to open-label SAR442168 treatment, he/she will need to be monitored for liver function tests after the first open-label dose at Weeks 2, 3, 4, 5, 6, 7, 8, 9, 10, 11, and 12, and then monthly for the next 9 months. After that, the schedule visits timepoints per SoA will be resumed (ie, every 3 months), until the common study end. Whenever a timepoint will coincide with a scheduled visit as per SoA (Section 1.3), the full scheduled visit assessments will be performed instead of the liver monitoring testing alone.

For participants achieving 6-month CDP, the Investigator must ensure that the participant does not meet any of the following criteria prior to the switch to open-label SAR442168 treatment:

• Current alcohol intake >2 drinks per day for men and >1 drink per day for women (1 drink = approximately 14 grams of alcohol = 350 mL beer = 140 mL wine = 40 mL of spirits).

- Acute liver disease, cirrhosis, chronic liver disease (unless considered stable for >6 months).
- Confirmed ALT >1.5 × ULN OR AST >1.5 × ULN OR ALP >2 × ULN (unless caused by non-liver-related disorder or explained by a stable chronic liver disorder) OR total bilirubin >1.5 × ULN (unless due to Gilbert syndrome or non-liver-related disorder).

Liver function tests will be performed for all participants prior to the start of open-label treatment.

Should the participant and Investigator opt for the provision of open-label medicine, they will remain blinded to the original treatment assignment.

All individual blinded data will be reviewed and all queries resolved, if possible, before the switch to the open-label treatment to ensure data integrity for primary assessment. Prior to initiation of open-label treatment, the Investigator shall confirm that there has been no adjudicated relapse within 90 days prior to the onset or confirmation of 6-month CDP. Based on individual symptoms and assessed risk of further progression, the Investigator and participant may choose for the participant to remain on the initial double-blind treatment after achieving 6-month CDP.

The initial treatment assignment will be kept blinded from participants, any Investigator site staff, and the Sponsor until the study end.

The supply of SAR442168 as open-label medication will be specified at the country level.

Multiple sclerosis relapses are not frequent in the NRSPMS population, but their occurrence during the study cannot be ruled out completely. In the case of MS relapse, treatments are allowed as per local routine practice (eg, high dose IV methylprednisolone for 3 to 5 days). The date and time of relapse treatment administration as well as the name and dosage regimen of the medication must be recorded.

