2.1 STUDY RATIONALE

The goal of this Phase 3 clinical trial is to demonstrate the efficacy and safety of SAR442168 compared to placebo in participants with NRSPMS. SAR442168 is a small molecule administered as a once daily oral treatment that is an irreversible, covalent inhibitor of BTK. SAR442168 is a brain-penetrant compound that modulates the pro-inflammatory activity of B cells in the periphery and in the CNS as a result of the BTK inhibition. The proposed mechanism of action for SAR442168 is to inhibit the coupling of the B cell receptor to downstream signaling in B cells, thereby modulating B cells without depleting them. Additionally, it is also known that activated B cells are key players in the pathogenesis of MS, specifically in the progressive form of the disease.

The immune complex receptor $Fc\gamma RII$, found in macrophages and microglial cells and that also signals through BTK, will similarly be modulated. The Sponsor hypothesizes that this action will result in a decrease of inflammatory activity in the CNS, diminishing brain lesions as detected by MRI as well as reducing the accumulation of disability progression.

The advent of disease-modifying therapies for relapsing forms of MS has led to significant strides in reducing relapse frequency and the attendant morbidity for people with MS. However, chronic disability accumulation remains a significant unmet need for people living with MS. Individuals with progressive disease, including SPMS, need therapies to reduce the accumulation of disability. With several drugs approved for active secondary progressive disease, there is still no treatment available for NRSPMS.

Data from the recent pivotal trial of siponimod, a S1P receptor modulator, in SPMS patients demonstrated reduced risk of 3-month confirmed disability progression (HR=0.79) (1). Data from ORATORIO, the pivotal Phase 3 trial of ocrelizumab in a PPMS population, demonstrated that this anti-CD20 monoclonal antibody that depletes B lymphocytes could provide a small but statistically significant benefit (HR=0.76) in reducing the risk of disability progression (2).

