4.2.2 Justification for the use of placebo

This study will explore the efficacy and safety of SAR442168 in participants that are not routinely included in MS clinical trials: NRSPMS patients. This study will allow for a proper controlled data driven approach in a subset of MS patients who do not have approved therapeutic options.

Data obtained in recent MS clinical trials also support the use of placebo as a comparator in this target population. The results from the Phase 3 EXPAND study (4), that explored the efficacy and safety of siponimod in SPMS participants, did not show a significant impact of this compound on disability progression in the sub-population of participants without relapses. For this reason, EMA approved siponimod only for active SPMS, characterized by recent relapse or MRI activity. In addition, ocrelizumab, the only DMT approved for primary progressive MS, has not been studied in NRSPMS (2, 28). Despite the off-label use of other DMTs for NRSPMS patients, clinical experience has confirmed a relative lack of efficacy for patients with low or absent clinical or MRI activity.

With the current study design, participants will be allocated 2:1, SAR442168 to placebo, in order to minimize the exposure to placebo and maximize the chance of receiving active therapy. The participants who enroll in the study and achieve disease progression (6-month CDP) will be offered treatment with open-label SAR442168 or the possibility to switch to another DMT, if available for NRSPMS in their country. All participants who successfully complete the study will additionally be offered the possibility to enroll in a long-term safety study where open label SAR442168 will be provided.

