7 DISCONTINUATION OF STUDY INTERVENTION AND PARTICIPANT DISCONTINUATION/WITHDRAWAL

7.1 DISCONTINUATION OF STUDY INTERVENTION

7.1.1 Definitive discontinuation

The study intervention should be continued whenever possible.

Permanent intervention discontinuation is any treatment discontinuation associated with the definitive decision by the Investigator or the participant not to re-expose the participant to the study intervention at any time.

In rare instances, it may be necessary for a participant to permanently discontinue the study intervention. If study intervention is permanently discontinued, the participant will be asked to remain in the study to be evaluated until the EOS visit. For this set of participants (participants who discontinued the IMP and/or switched to other DMTs), no PK or biomarker samples will be collected after the pEOT visit, and MRI assessments will be performed only annually using the next annual visit as the starting point.

This will be important to continue to evaluate for safety and efficacy. See the SoA (Section 1.3) for data to be collected at the time of discontinuation of the study intervention. In the case that the study intervention is permanently discontinued, the participant should be treated for MS according to local clinical practice and the best judgment of the Investigator.

The following may be justifiable reasons for the Investigator or Sponsor to discontinue a participant from treatment:

- Adverse events that endanger the safety of the participant, or if discontinuation of study intervention is desired or considered necessary by the Investigator and/or participant.
- If IMP discontinuation criteria are met as per the guidance for the follow up of laboratory abnormalities (Appendix 2 [Section 10.2]).
- The participant is no longer deriving a therapeutic/clinical benefit in the opinion of the Investigator.
- If a female participant becomes pregnant or wishes to become pregnant during the study.
- At participant's request, ie, withdrawal of the consent for treatment.
- Any serious opportunistic infections (eg, PML [see Appendix 6 {Section 10.6}], HIV)
- Continued need for/chronic use of prohibited a concomitant medication (see Appendix 9 [Section 10.9]).
- Use of open-label SAR442168 or non-study disease modifying therapy approved for NRSPMS in their respective countries (eg, after 6-month CDP).

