Change from baseline in SDMT number of correct substitutions, CVLT-II total correct and MSQoL-54 physical and mental health composite scores at the EOS will be analyzed using an analogous MMRM approach in the ITT population with the change from baseline values for the respective endpoint at scheduled visits up to and including the EOS visit as response variables, and treatment group, age at screening (>40,  $\leq$ 40 years), geographic region (US, non-US), visit, treatment-by-visit interaction, baseline value for the endpoint being assessed and baseline value-by-visit interaction as covariates.

For each endpoint, difference in LSM, the corresponding 95% CI, and p-value will be estimated from the MMRM model for the comparison of tolebrutinib to placebo using weights for each stratum equal to the overall proportion of participants in each stratum (ie, "Population weight"). Plots of LSM [±standard error (SE)] over time will be provided. Participants who discontinue study intervention before the study end will be asked and encouraged to return for all remaining study visits and the additional off-treatment values measured up through the EOS will be included in the primary analysis. For participants who withdraw from the study before the EOS, values will be missing after study discontinuation and no imputation will be performed.

SDMT, CVLT-II and MSQoL-54 data are assumed a priori to be normally distributed. Given the large sample size, the impact of violation of normality should not be great. In order to assess the impact of deviation from the normality assumption, a sensitivity analysis using rank analysis of

covariance (ANCOVA), with the same covariates as for the MMRM analysis except VISIT and related interaction terms, will be performed to test the significance of the treatment effect.

Given that participants who reach the primary endpoint of 6M-CDP are eligible to switch to OL tolebrutinib, including data after the switch could impact the analysis of secondary endpoints: number of new/enlarging T2 lesions per year, time to onset of sustained 20% increase in the 9-HPT (T25-FW) for at least 3 months, and percent change in brain volume at EOS compared to Month 6. Sensitivity analyses excluding data after initiation of OL therapy will be performed for these endpoints.

No other sensitivity, supplementary, or subgroup analyses will be performed for the secondary endpoints.

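### The protocol words the post-CDP switch to a non-study MS drug inconsistently, and the SAP sensitivity analyses that remove post-switch data cut only at open-label tolebrutinib

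*Protocol*

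**What the plan says.** **Switch rule.** Protocol 6.6.1 gives a participant with 6-month CDP two switches: open-label tolebrutinib, or "To switch to a non-study treatment approved for NRSPMS in their respective country". It also allows staying on double-blind treatment. For the second switch, "the participant will permanently discontinue the IMP and will be encouraged to remain in the study for planned clinical visits (see Section 7.1.1". The list of discontinuation reasons in 7.1.1 repeats the condition: "non-study disease modifying therapy approved for NRSPMS in their respective countries (eg, after 6-month CDP".

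**Rationale text.** Protocol 4.2.2 describes the same choice as "the possibility to switch to another DMT, if available for NRSPMS in their country". The section also says that this population has no approved options and acknowledges off-label DMT use.

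**General discontinuation text.** For any permanent IMP discontinuation, 7.1.1 says that "the participant should be treated for MS according to local clinical practice and the best judgment of the Investigator", and repeats this in its paragraphs on handling after discontinuation. It sets no approval condition. Section 6.6 bars the E 06 therapies only during study treatment.

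**Options that exist.** Protocol 2.1 states that "there is still no treatment available for NRSPMS".

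**Analysis.** SAP 3.3.1.2.3 reasons that the switch to open-label tolebrutinib after 6-month CDP could affect T2 lesions, 9-HPT, T25-FW and brain volume, and concludes: "Sensitivity analyses excluding data after initiation of OL therapy will be performed for these endpoints". Protocol 9.4.3 likewise refers only to open-label therapy.

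**The concern.** A site reading 6.6.1 and a site reading 7.1.1 can reach different answers about what a participant who has progressed and stopped IMP may receive. The protocol expects some of this switching: 7.1.1 and 8.6 both set procedures for participants who moved to other DMTs. They are asked to stay in the study, with annual MRI, so outcome data collected on the other drug will exist.

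The SAP's sensitivity analyses deal with one of the two switches triggered by 6-month CDP and leave the other in. More placebo than tolebrutinib participants, as a proportion, are expected to progress, so the contamination need not be equal between arms. The four endpoints concerned are four of the six secondary endpoints in the testing hierarchy (SAP 3.5). SAP Appendix 3 tabulates post-treatment medications, but no efficacy analysis uses them.

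**Working it through.** **1. The wordings side by side**

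| Place | Condition on the non-study drug | Who qualifies, by the protocol's own statements |
|---|---|---|
| 6.6.1 and the 7.1.1 list | approved for NRSPMS | essentially nobody (4.2.2: no approved options) |
| 4.2.2 | available for NRSPMS | essentially nobody (2.1: none available) |
| 7.1.1, general text | local practice and Investigator judgment | any progressor who stops IMP, in either arm |

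The wide gap is between the first two rows and the third.

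**2. The plan's own figure.** Inputs from Protocol 9.2: 288 events, HR 0.70, 2:1 allocation, two-sided α = 0.05. By Schoenfeld, √(288 × 1/3 × 2/3) × |ln 0.70| − 1.96 = 8 × 0.3567 − 1.96 = 0.893, which is a power of 81.4% against 80% stated. The same formula needs 278 events for 80%, so 288 is slightly conservative.

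**3. How many reach 6-month CDP.** Further inputs from 9.2: 23.6% placebo events at 2 years, 10% annual discontinuation, 24 months of accrual and 24 months of minimum follow-up (taken as 2 years each), N = 1290 (430 placebo, 860 tolebrutinib).
- Placebo hazard λ = −ln(1 − 0.236)/2 = 0.1346 per year; tolebrutinib 0.70 × 0.1346 = 0.0942.
- Discontinuation hazard δ = −ln(0.9) = 0.105 per year.
- Probability of an onset within follow-up F: λ/(λ+δ) × [1 − exp(−(λ+δ)F)], averaged over F uniform on 2 to 4 years. This gives 28.5% (123 of 430) and 21.1% (181 of 860), 304 in total.
- Placebo share of events: 40.3%. Scaled to 288 events: about 116 placebo (116/430 = 27%) and 172 tolebrutinib (172/860 = 20%).
- Fallback of N = 1100 with 30 months' minimum follow-up: 31.6% and 23.6%, about 289 events by onset.

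**4. Follow-up time after confirmation.** Confirmation lag L = 168/365.25 = 0.46 year (6 months of 28 days). Per-participant time after confirmation is the integral from t = 0 to F − L of λ·exp(−λt)·[exp(−δ(t+L)) − exp(−δF)]/δ. This is averaged over F and divided by the average total follow-up, [1 − exp(−δF)]/δ. The result is 12.5% of placebo and 9.0% of tolebrutinib follow-up time if every progressor switched at confirmation (14.7% and 10.7% in the N = 1100 fallback). None of this time would be removed by a cut at open-label therapy.

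**5. Illustration for T2 lesions, with assumed values.** Suppose a true tolebrutinib:placebo rate ratio of 0.50 and a lesion rate on the non-study DMT of 0.3 to 0.5 times placebo, with every progressor switching.
- DMT at 0.5: placebo 0.875 + 0.125 × 0.5 = 0.9375; tolebrutinib 0.5 × 0.910 + 0.090 × 0.5 = 0.500; ratio 0.53.
- DMT at 0.3: placebo 0.9125; tolebrutinib 0.482; ratio 0.53.

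If half switched, the ratio would be 0.51 to 0.52.

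**The case against.** A reader might infer that the protocol holds three competing switch rules. It does not. The operative rule says *approved* in both places where it is stated as a rule. Section 4.2.2 is a justification for placebo. The local-practice sentence is general guidance for any permanent discontinuation and reaches CDP switchers through the reference in 6.6.1, which is attached to remaining in the study. *Available* also does not open the door, given 2.1. All of this stands. It narrows the conflict to the general text of 7.1.1 against the other passages, plus one inconsistent word in 4.2.2. That word is not idle: the amendment history records that the sponsor replaced *available* by *approved* in the switch rule at Amended protocol 01.

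A second objection is that the SAP does what Protocol 9.4.3 asks, namely assess the impact of open-label therapy, and that the main analyses of the continuous endpoints keep off-treatment values by design. That also stands: the SAP does not breach its parent section. But the stated reason, that post-CDP switching could affect these four endpoints, applies equally to the second switch in 6.6.1.

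Third, 4.2.2 itself reports a relative lack of efficacy of other DMTs in patients with little disease activity, and a drug that did help placebo progressors would tend to dilute the comparison. Both support a modest rating.

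**Conclusion.** The passages conflict on what a participant may receive after 6-month CDP, and the sensitivity analyses leave data after a non-study DMT in place. The size is limited. The 27% of placebo and 20% of tolebrutinib are progression figures. They bound post-CDP switching only if every progressor declines both open-label tolebrutinib and continued blinded treatment, and they should not be read as an expected share or as a placebo-only issue. The documents give no uptake figure. The shares of follow-up time, 12.5% and 9.0%, rest on constant hazards, the planning rates, N = 1290 and an immediate switch at confirmation.

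A reader might also infer a threat to the primary result. The documents do not support that: this switch follows confirmed 6-month CDP, by which time the primary event and 3-month CDP have both occurred. What remains is a clarity problem for sites and a modest, inexpensive improvement to sensitivity analyses of four hierarchy endpoints.

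**What to change.** - **Protocol.** Reconcile 4.2.2, 6.6.1 and both local-practice statements in 7.1.1, so that one rule says which non-study treatments may be started after 6-month CDP and how the general discontinuation text applies to those participants. The sponsor decides the content.
- **SAP 3.3.1.2.3, with Protocol 9.4.3 aligned.** In the existing sensitivity analyses, exclude data after the earlier of the first open-label tolebrutinib dose or the start of any non-study MS DMT. State that the cut applies whether or not the DMT followed CDP. The main analyses do not change.
- **Reporting.** Give the number of participants in each arm who switched to open-label tolebrutinib and to a non-study DMT.

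The cost is wording in the next amendment, one phrase in the SAP and one table. Concomitant medication start and end dates are already recorded under Protocol 6.6. The downside is slightly less data in the sensitivity analyses.
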